The Brief Problem Monitor (BPM), a short version of the Child Behaviour Checklist (CBCL; Achenbach & Rescorla, 2001), will be used to measure parent-reported child behavioural problems. While both versions have been used extensively in research, the 113 item CBCL is too long to repeat regularly. The BPM is more suitable than the alternative Strengths and Difficulties Questionnaire (SDQ; Goodman, 1997) because of the difference in factor structures; the externalising scale of the BPM is more consistently supported in factor analyses than the five-factor structure of the SDQ which has externalising behaviour represented across three different subscales (McCrory & Layte, 2012).

SECONDARY ENDPOINTS/OUTCOMES

The secondary measures include a parenting practice measure, parental reflective functioning measure, a general wellbeing measure and an ideographic measure to capture parents' perception of the problems and assess any change. A change interview will also be completed with participants.

Parenting practice measure

The Multidimensional Assessment of Parenting Scale (MAPS) uses a two-factor structure that assesses positive (e.g. nurturing, attuned) and negative (e.g. hostile, punitive, critical) parenting practices (Parent & Forehand, 2017). The MAPS takes approximately ten minutes to complete every session, which is a time burden for participants. There are very few alternatives, however, that are shorter and retain adequate psychometric properties. Relying on a self-report measure without observations of parenting is a limitation, although there is evidence to suggest that self-report measures of parenting do correlate with independent observations (Hawes & Dadds, 2006). An observational element is not included because this would impact the feasibility of the study in the given timescale, particularly in the context of the global pandemic. The MAPS will be shortened for repeated measurement purposes. This will be done by taking the top 3 items from the MAPS positive scale and the top 3 from the negative and using that as a proxy process measure. What constitutes 'top' can be established by either face-validity, relative factor loadings of each item derived from the original scale development, or a combination of both.

Parental reflective functioning measure

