Across both sites the referred children of participants will remain on the waiting list, with an allocated lead professional, for the duration of the intervention. Consequently, the services will retain clinical responsibility throughout the intervention. When potential participants are identified by staff from the services, in the first instance the allocated lead professional will establish if parents/carers consent to being contacted for research purposes. If consenting to the contact, the doctoral student will then contact potential participants – see Study Procedure below for full details. Staff from the service will have no further role in the research study. However, notes from the intervention sessions will be uploaded to the record of the referred child for each service meaning staff can access session notes if they have a legitimate reason to do so. This will be made clear to participants at the outset of the study.

SELECTION OF PARTICIPANTS

ELIGIBILITY CRITERIA

Participants will be parents/carers of children who have been referred to NHS children's services for behavioural problems. Participants will be recruited from waiting lists of NHS children's services as outlined above.

Inclusion Criteria

- The referred child is aged between three and eleven years old.
- The referred child is on a waiting list for an NHS children's service in the primary or secondary study site.

- The referred child's behavioural problems are one of the primary reasons for referral to the NHS service.
- The parent/carer identifies the referred child's behaviour as problematic.

NICE guidelines only recommend parent-focused interventions for behavioural problems with children aged between 3 and 11 years old (NICE, 2017). Child behavioural problems are an important focus of this research, hence the requirement for the referred child's behaviour to be one of the primary reasons for referral. The requirement for children to be on a waiting list for an NHS children's service means that the child and parent will be able to access treatment as usual regardless of this research and will retain an allocated lead professional from the service though the intervention. Finally, the parent/carer needs to identify the behaviour as problematic; otherwise, a guided self-help intervention would not be appropriate.

Exclusion Criteria

- The referred child has a diagnosis of developmental delay or learning disability.

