All participants shall provide written informed consent. The ICF will be signed and dated by the participant before they enter the study.

Potential participants will have been given the PIS by the member of the referred child's usual care team. Potential participants will be given a minimum of 24 hours to consider their participation before they are

contacted by a member of their usual care team to give their verbal consent for their contact details to be passed onto the research team.

The recruiting investigator (the doctoral student) will explain the details of the study and ensure participants have a PIS (and any other study related literature), making sure that the participant has sufficient time to consider participating or not. Opportunity will be given to the participant to ask any questions they may have concerning study participation. Participants will be asked to consent to the research team accessing their child's medical record for the researcher to create a note on the child's record following each guided self-help session. It is usual practice for any clinical contact to be logged by the person making the contact, in this case the researcher, as soon after the contact as possible. By having access to the medical record, the researcher can upload the note directly after the session which is good practice and particularly important if any safeguarding issues are identified.

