The participant no longer meets the eligibility criteria for the study. The researcher informs them and the participant is withdrawn from the study.

The participant completes the intervention phase and continues to the follow-up phase.

Follow-up Phase

The researcher will contact the participants to complete the questionnaires for the last time and arrange a follow-up interview with an independent researcher. The follow-up interview is the participant's chance to give feedback on the intervention and how you found it.

The participant decides they do not want to continue taking part in the study and informs the researcher.

After taking part in the interview, the participant has completed the study and will be sent an overview of the research unless they have opted out.

STUDY REGIMEN

The screening procedure is outlined above in the eligibility, recruitment and consent sections.

Baseline phase

Following informed consent, participants will begin the baseline phase. During the baseline phase, participants will be contacted twice a week by phone by the doctoral student to collect the data. The table below shows the frequency of administration for each measure throughout the study. The exact timing of phone calls will be organised with each participant around their availability and the availability of the doctoral student.

The necessity to complete multiple measures will be made clear to participants both in the initial conversation and PIS. If participants do not consistently complete the measures, the researcher will speak to the participant to identify why and explain the impact on the research. If measures continue not to be completed during the baseline phase, participants may be withdrawn from the study.

If stability is not achieved on any variable, participant data will be considered on a case-by-case basis. Lack of stability likely to undermine the validity of subsequent results may result in participants being withdrawn from the study. However, because each participant acts as their own control, a limited amount of variability may not have a significant impact on the study (Kratochwill et al., 2010).

Intervention phase

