The intervention phase will exclusively use the official NHA self-help workbook (Glasser, 2016); a workbook will be purchased for each participant by the research team using the research budget. The doctoral student will also undertake the six-hour NHA online training course produced by the creators of the NHA (Glasser & Easley, 2016). This is to ensure that the guided aspect of the intervention is completed with as much fidelity to the approach as possible.

A chapter from the book will be sent to the participants each week through the post. Each participant will be requested to read the chapter prior to the arranged guided self-help session. The doctoral student will then contact the participant by phone to complete the guided self-help session which involves discussing the prompt questions provided in the workbook. The exact timing of phone calls will be organised with each participant based around their availability, the availability of the doctoral student and when they received the workbook in the post. Process measures will be collected at the beginning of this phone call. These sessions will be audio-recorded.

If participants do not read the chapter in advance of the phone call, the option will be given to the participant to read through the chapter jointly during the call, including prompt questions, or to postpone the phone call by a day. Flexibility will be prioritised as the time-intensive nature of the intervention is recognised. However, if participants do not attend the six intervention sessions, they will be withdrawn from the study as they will not be receiving the intervention in a standardised way.

One month post intervention, the participants will be contacted again to complete all five measures and arrange the change interview. The measures will be completed by the doctoral student. The change interview will be completed by a second doctoral student who will not previously have been involved in the study; this interview will also take place via phone and will be audio-recorded.

Frequency of measure collection

Measure	Baseline (A)						Intervention (B)												Follow-up
	Week 1		Week 2		Week 3		Week 4		Week 5		Week 6		Week 7		Week 8		Week 9		Week 13
	Day 1	Day 4	Day 1	Day 4	Day 1	Day 4	Day 1	Day 4	Day 1	Day 4	Day 1	Day 4	Day 1	Day 4	Day 1	Day 4	Day 1	Day 4	Day 1
Short Warwick-Edinburgh Mental Wellbeing Scale (SWEMWBS)	✓																	✓	✓
Psychological Outcomes Profiles (PSYCHLOPS)	✓																	✓	✓

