The study was reviewed as part of the academic requirements for the DClinPsy course that the doctoral student is undertaken. The feedback from the peer review by university academic staff is detailed in the scientific critique document.

PUBLIC & PATIENT INVOLVEMENT

Input will be sought by the service user and carer advisory panel (SUCAP) attached to the Trent DClinPsy programme. Initial input from SUCAP members shaped the formation of the research idea in the early stage of development (January 2021). Additionally, parents/carers have been consulted to check the readability and suitability of the participant information sheet, consent form and interview schedules.

PROTOCOL COMPLIANCE

Accidental protocol deviations may occur at any time. Accidental protocol deviations will be adequately documented on the relevant forms and reported to the Chief Investigator and Sponsor immediately.

Deviations from the protocol which are found to frequently recur are not acceptable, these will require immediate action and could potentially be classified as a serious breach.

DATA PROTECTION AND PATIENT CONFIDENTIALITY

All study staff and investigators will comply with the principles of the General Data Protection Regulation (GDPR) 2016/079 in protecting the rights of study participants with regards to the collection, storage, processing and disclosure of personal information and will uphold the Act's/Regulations core principles.

Each participant will be assigned a participant identification code, for use on study records, other study related documents and the electronic database. Personal data, as defined under the Data Protection Act, will include participant demographics, contact details, signed consent forms, recordings of intervention sessions and

recordings and transcripts of change interviews. Completed measures will not be personally identifiable as an anonymised participant identification code will be used.

Personal data, research data and the linking code will be stored in separate locations. When stored electronically, this will include using encrypted digital files within password protected folders and storage media. Personal information shall be stored separately to research data and will be kept secure, and maintained.

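### Intervention-phase questionnaires are taken on a recorded call that is followed by a note in the child's record, with no such conditions described at baseline, so a reporting shift in negative parenting could coincide with the phase change

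*Combined protocol and SAP*

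**What the plan says.** **Intervention calls.** The Study Regimen section (Intervention phase) has the doctoral student telephone the parent each week for the guided self-help session, and adds: "Process measures will be collected at the beginning of this phone call. These sessions will be audio-recorded".

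**Session notes.** Under Consent, parents agree to record access "for the researcher to create a note on the child's record following each guided self-help session". Study Setting says that "notes from the intervention sessions will be uploaded to the record of the referred child for each service meaning staff can access session notes", given a legitimate reason, and continues: "This will be made clear to participants at the outset of the study".

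**Baseline calls.** These are described only as data collection: "participants will be contacted twice a week by phone by the doctoral student to collect the data". No recording or note is mentioned. The personal-data list under Data Protection includes "signed consent forms, recordings of intervention sessions and" then those of the change interviews; baseline or follow-up measures calls are not on it.

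**The sensitive measure.** The MAPS "assesses positive (e.g. nurturing, attuned) and negative (e.g. hostile, punitive, critical) parenting practices". The same section concedes: "Relying on a self-report measure without observations of parenting is a limitation".

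**Analysis.** Graphs of the process measures are inspected for whether and when change occurs. The Reliable Change Index and clinical significance follow.

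**The concern.** In an A-B design, anything that changes together with the phase is confounded with the intervention. Here the circumstances in which a parent answers appear to change at that point. At baseline the parent answers on a call made only to gather data. From the first intervention reading, the same questions come at the start of a session that is recorded and then written up in the child's record. Its potential readers work for the service on whose waiting list the child remains.

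Some MAPS items ask about hostile, punitive or critical parenting. A parent may be less ready to admit to these under the second set of conditions. Under-reporting that began there would appear as a drop at the phase change, which is the pattern visual analysis would credit to the intervention under question 1a. No observational measure of parenting is planned that could expose it, and it could not be corrected after data collection.

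**Working it through.** The plan states no figure on this point, so there is none to reproduce. The check has three steps.

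**1. Count readings by condition** (Frequency of measure collection table; MAPS, PRFQ and BPM share one pattern).

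| Phase | Readings | Recording described | Record note described |
|---|---|---|---|
| Baseline, weeks 1–3 | 6 | no | no |
| Intervention, weeks 4–9 | 6 | yes, for the session | yes, after each session |
| Follow-up, week 13 | 1 | only for the separate change interview | no |

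So 6 of 6 intervention readings and, as far as the text shows, 0 of 6 baseline readings are attached to a recorded and noted session. Lengthening one participant's baseline moves both the intervention and the change of conditions, so the multiple-baseline feature does not separate them.

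**2. What a pure reporting shift could do to the graphs.** Assumptions: no true effect; 6 + 6 independent normal readings of equal variance; a constant downward shift s in all six intervention readings, in within-person SD units; 200,000 simulated cases. The marker is at least 5 of 6 intervention points below the participant's baseline median. The protocol sets no such rule; it only stands in for a visible drop. With p the per-participant probability of the marker, the chance that at least 3 of 6 participants show it is the sum over k = 3 to 6 of C(6,k) p^k (1−p)^(6−k). Three is the number the Size of sample section gives as the minimum to demonstrate an effect.

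| s | p | At least 3 of 6 participants |
|---|---|---|
| 0 | 0.18 | 0.08 |
| 0.25 | 0.29 | 0.24 |
| 0.5 | 0.42 | 0.50 |
| 1.0 | 0.70 | 0.93 |

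On the shortened MAPS, with three negative items, one point less on one item moves the item mean by 1/3 = 0.33.

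**3. What it could do to the Reliable Change Index.** The threshold is 1.96 × √(2(1−r)) reference-sample SDs. The documents give no reliability r, so a range is assumed:

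- r = 0.7: 1.96 × √0.6 = 1.52
- r = 0.8: 1.96 × √0.4 = 1.24
- r = 0.9: 1.96 × √0.2 = 0.88

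A shift acting alone would have to be that large. These are reference-sample SDs, whereas step 2 uses within-person SDs. To put both on one scale, assume that within-person variation is measurement error only. The threshold is then 1.96 × √2 = 2.77 within-person SDs, and the difference between two single readings has SD √2 = 1.41. The chance of a falsely reliable improvement is the upper normal tail at (2.77 − s)/1.41:

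- s = 0: z = 1.96, 2.5%
- s = 0.5: z = 1.61, 5.4%
- s = 1.0: z = 1.25, 10.5%

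At s = 0.5 the false signal rises from 2.5% to 5.4% on the index, against 18% to 42% on the graphical marker.

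**The case against.** Several points on the other side stand.

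- **Parents already know.** They are told of the notes at the outset, before the first score. The same student collects the scores in both phases, and the safeguarding route applies throughout. This may well shrink any step, but does not remove it: what parents are told is that intervention-session notes are uploaded, which itself marks those calls as different.
- **It is not stated that the answers are recorded or noted.** The recorder might start after the questionnaires, and nothing says that scores enter the note. Completed measures are coded. As written, though, the measures belong to a call whose session is recorded, and coding the forms does not cover spoken answers.
- **The baseline condition rests partly on silence.** Consent calls it usual practice to log any clinical contact. However, it ties the note to guided self-help sessions, and the list of recordings supports the reading that baseline calls are not recorded.
- **The information sheet is not among the documents** and may already settle this, so its silence cannot be assumed.

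A reader might also infer that the primary outcome is biased towards benefit. The documents do not support that. The BPM rates the child, these parents already regard the behaviour as problematic, and being visible to the service they are waiting for could prompt fuller reporting. Nor can a worse week-13 score be put down to a return of candour: the conditions of that call are only inferred, and a single reading cannot separate candour from a fading effect.

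**Conclusion.** The concern holds as an avoidable, phase-linked difference in disclosure conditions. It bears mainly on self-reported negative parenting (MAPS negative scale, question 1a). It does not show that the results will be biased, and it gives no direction for the BPM.

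The size is unknown. The illustration assumes independent readings and a shift that stays constant through the intervention phase; parents may instead get used to being recorded. Under those assumptions, 0.25 to 0.5 within-person SD lifts the chance of a visible drop in one participant from 18% to between 29% and 42%. The marker is not the protocol's and already occurs in 18% of null cases, so the increase matters more than the level. Visual analysis is more exposed than the Reliable Change Index.

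The protocol should be changed, because the remedy is cheap and the confound cannot be undone later. Confidence is medium, given what is inferred about the baseline calls and what the information sheet may say.

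**What to change.** 1. In the intervention phase, collect the measures before the recorder is switched on, and say so in the Study Regimen section.
2. State that questionnaire answers and scores are not entered in the session note.
3. Read parents the same short statement on recording, notes and use of their answers at the start of every measures call in baseline, intervention and follow-up. Say explicitly whether baseline and week-13 calls are recorded or noted.
4. Leave the existing safeguarding procedure unchanged; it already covers all phases.

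The cost is a short protocol change and a later start to each recording, with no extra staff or data. If the information sheet is already approved and needs a matching sentence, the Ethics Review and Compliance section requires ethics committee approval before the change takes effect. If the procedure cannot be changed, report the difference as a limitation on question 1a.

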The process for obtaining participant informed consent will be in accordance with the REC guidance, and Good Clinical Practice (GCP) and any other regulatory requirements that might be introduced. The investigator or their nominee and the participant shall both sign and date the ICF before the person can participate in the study. Participants will be able to sign the ICF electronically or can sign, scan and send back the form electronically. One copy of the ICF will be kept by the participant, one will be kept by the research team, and a third will be retained in the referred child's medical records. It will be explained to the potential participants that participation in the research study will not impact the treatment as usual that they receive from the service for which the referred child is on a waiting list. Participants will be given the contact details of the research team should they have any further questions. Should there be any subsequent amendment to the final protocol, which might affect a participant's participation in the trial, continuing consent will be obtained using an amended consent form which will be signed by the participant. Capacity will be assumed for all participants as they will be adults (over the age of 18).

[figure not shown]
STUDY PROCEDURES/REGIMEN

STUDY FLOWCHART

Below are the study flowcharts written for the participant. The first explains the process of recruitment, the second explains participation in the intervention.

Flowchart

Recruitment.

Baseline Phase

The researcher contacts the participant twice per week to collect information using questionnaires (also called measures). This phase is likely to last three weeks but may be slightly longer.

The participant decides they do not want to continue taking part in the study, informs the researcher and is withdrawn from the study.

The participant no longer meets the eligibility criteria for the study. The researcher informs them and the participant is withdrawn from the study.

The participant completes the baseline phase and continues to the intervention phase.

Intervention Phase

The participant will be sent one chapter of the workbook to read each week. The researcher contacts the participant once a week to collect information using questionnaires and discuss the chapter. This phase lasts six weeks.

The participant decides they do not want to continue taking part in the study, informs the researcher and is withdrawn from the study.

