Multidimensional Assessment of Parenting Scale (MAPS)	✓	✓	✓	✓	✓	✓		✓		✓		✓		✓		✓		✓	✓
Parental Reflective Functioning Questionnaire (PRFQ)	✓	✓	✓	✓	✓	✓		✓		✓		✓		✓		✓		✓	✓
Brief Problem Monitor (BPM)	✓	✓	✓	✓	✓	✓		✓		✓		✓		✓		✓		✓	✓

SCHEDULE OF PROCEDURES

Procedures	Sessions			
	Screening	Baseline (weeks 1-3)	Intervention (weeks 4-9)	Follow up (week 13)
Informed consent	x			
Demographics		x		
Measure collection		x	x	x
Intervention			x	
Change interview				x

WITHDRAWAL

Participants may be withdrawn from the trial either at their own request or at the discretion of the investigator (with input from the whole research team). The participants will be made aware that this will not affect their future care. Participants will be made aware (via the information sheet and consent form) that should they withdraw the data collected to date may not be erased in accordance with the University's Research Privacy Notice and information given in the Participant Information Sheet and may still be used in the final analysis.

Participants who withdraw prior to starting the intervention will be replaced. After starting the intervention phase, replacement of participants will be considered on a case-by-case basis depending on individual circumstances. If a participant withdraws before the start of the intervention phase, they will not receive the self-help workbook, but will be made aware that they can purchase the book themselves.

ETHICAL AND REGULATORY CONSIDERATIONS

ASSESSMENT AND MANAGEMENT OF RISK

If information is disclosed during the study that could pose a risk of harm to the participant or others, the researcher will discuss this with the CI and where appropriate report accordingly.

Risks will be managed in accordance with each trust's safeguarding policy. The Health and Care Professions Council (HCPC) practitioner psychologist guidance will also be adhered to. During participation in the study, the doctoral student may become aware of harm being caused to the referred child or other children. If a disclosure or concerns about a child are raised, the trust policies will be followed and the referred child's usual care team and the chief investigator will be informed at the earliest possible opportunity.

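### Parents who do not attend the six sessions are to be withdrawn, with no route to week-13 measures or the change interview and no rule for reporting their partial series

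*Combined protocol and SAP*

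**What the plan says.** Study Regimen, Intervention phase, states that "if participants do not attend the six intervention sessions, they will be withdrawn from the study". The reason given is that delivery would not be standardised. The same paragraph lets a parent who has not read the chapter go through it during the call or postpone by a day, and adds that "Flexibility will be prioritised as the time-intensive nature of the intervention is recognised". It does not define non-attendance or say when withdrawal takes effect.

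The Withdrawal section is permissive: "Participants may be withdrawn from the trial either at their own request or at the discretion of the investigator". It says data collected up to withdrawal may be kept and may be used in the final analysis. Recruitment says consent to that use will be sought where appropriate. Replacement after the intervention has started is decided case by case.

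The participant flowchart shows the route to week 13 as "The participant completes the intervention phase and continues to the follow-up phase", and says of the last contact that "The follow-up interview is the participant's chance to give feedback on the intervention and how you found it". Data Analysis plans framework analysis of the change interviews, and graphs plus reliable and clinically significant change for the measures. It does not mention incomplete series.

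**The concern.** Secondary question 2 asks how feasible and acceptable the approach is as guided self-help. Parents who miss sessions know best why it was not feasible or acceptable for them. The change interview is the only parent feedback with a planned analysis. Session notes and recordings exist up to withdrawal, but no analysis of them is planned. A rule that ends participation on non-attendance takes the interview away from these parents.

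The second issue is selection of cases. In a multiple baseline design the argument rests on how many cases replicate the effect. If nobody has fixed in advance whether a partial series is shown, or whether a replacement is added to the parent who left or takes that parent's place, the count of replications can be settled with the data in view.

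**Working it through.** **Reading the sections together**

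1. The Intervention phase text says non-attenders will be withdrawn; the Withdrawal section says participants may be. Whether withdrawal is automatic or a matter of judgement is therefore unclear.
2. Not attending the six sessions can mean missing any one of them or missing all of them. The consequences differ greatly.
3. Week-13 measures and the interview are described for participants one month after the intervention. The flowchart reaches them through completion of the intervention phase. No section offers either to a withdrawn parent.
4. Recruitment and Withdrawal permit use of data already held. Neither says whether a partial series is graphed, reported or counted as a case, or how reliable change is judged without an end point. Data Analysis does not fill the gap.

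**Data held on withdrawal**

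The inputs come from the Frequency of measure collection table. BPM, MAPS and PRFQ are each taken 6 times at baseline, 6 times in the intervention and once at follow-up: 6 + 6 + 1 = 13. SWEMWBS and PSYCHLOPS are taken 3 times (weeks 1, 9 and 13). The Intervention phase text adds that "Process measures will be collected at the beginning of this phone call", so I count a missed session as a missed reading.

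If withdrawal takes effect at first missed session k, readings held = 6 + (k − 1), of which k − 1 are intervention-phase:

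| k | Held of 13 | Intervention-phase |
|---|---|---|
| 1 | 6 | 0 |
| 2 | 7 | 1 |
| 3 | 8 | 2 |
| 4 | 9 | 3 |
| 5 | 10 | 4 |
| 6 | 11 | 5 |

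SWEMWBS and PSYCHLOPS stand at 1 of 3 throughout.

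If instead one missed session is judged at the end of the phase, 6 + 5 = 11 of 13 readings are held, 5 of them intervention-phase. SWEMWBS and PSYCHLOPS stand at 2 of 3, or 1 of 3 if the sixth session was the one missed.

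Under either timing there is no week-13 reading and no interview.

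**Share of interviews lost per parent**

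With six parents, 1/6 = 16.7%. At the fallback of three in Size of sample, 1/3 = 33.3%. The documents give no attendance or completion rate, so I claim no expected loss.

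**Extra contacts if such a parent is kept in follow-up**

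If the parent is not replaced, none beyond those already planned for six. If the parent is also replaced, the remaining contacts are (6 − k) measures calls + 1 week-13 call + 1 interview = 8 − k, which is 7 down to 2 for k = 1 to 6. If the missed session's measures are also made up, it is 9 − k, which is 8 down to 3.

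**The case against.** The strongest reply is that the sections can stand together. The Withdrawal section gives the investigator discretion, and the Intervention phase rule can be read as one use of it fixed in advance, with its reason stated. Flexibility is offered before withdrawal arises. Use of withdrawn parents' data is addressed in two places. Attendance and withdrawal counts remain as feasibility evidence, and disengaged parents may decline an interview anyway. Much of this stands, and it is why the point is modest. It does not supply a route to follow-up, a rule for partial series or a definition of non-attendance. Standardised delivery is a reason to label incomplete exposure; it is not a reason to stop measuring.

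Three stronger readings are tempting, and the documents do not support them.

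- A reader might infer that the flowchart contradicts the rule, because its intervention-phase exits are only that "The participant decides they do not want to continue taking part in the study, informs the researcher and is withdrawn from the study" and that "The participant no longer meets the eligibility criteria for the study". The flowchart is a simplified version for participants. Its baseline part shows the same two exits, although Study Regimen adds incomplete measures and lack of stability as grounds for baseline withdrawal. Omission there is not contradiction.
- A reader might infer that the plan is silent on partial data or discards them. It permits their use; what is missing is a firm inclusion rule.
- A reader might infer that a fourth loss from six, or a first from three, leaves too few cases. That assumes a partial series is not a case, which the plan leaves open. The fallback to three is also written for difficult recruitment, not for attrition.

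**Conclusion.** The point holds as a cheap improvement. Following the plan as written, interview evidence for secondary question 2 comes from completers only, at a cost of 17% of planned interviews per parent lost from six, or 33% from three. This rests on reading withdrawal from the study as ending all contact; no section says otherwise.

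For effectiveness, each remaining parent is their own control, so another parent's withdrawal does not bias that parent's A-B comparison. What is exposed is the number of replications shown and any summary across cases. The direction is unknown: parents may stop because the approach did not help, because of the time it takes, or because the problem improved. No figure in the plan is shown to be wrong.

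**What to change.** These changes concern data collection and reporting only. Whether sessions continue after non-attendance, and what counts as non-attendance, is for the sponsor to settle.

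1. Reconcile the Intervention phase and Withdrawal texts, define non-attendance and its timing, and separate stopping the sessions from leaving the study.
2. Unless the parent asks to leave, offer the remaining scheduled measures, the week-13 measures and the change interview. Record refusals.
3. State in Data Analysis that every participant with at least one intervention-phase reading is graphed and reported with sessions attended marked, within the consent given. Show six-session completers as a labelled secondary view. List parents with baseline readings only, with reasons.
4. Report any replacement in addition to the parent replaced.

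The cost is protocol, information sheet and consent wording. There are no contacts beyond those planned unless the parent is also replaced, when there are 2 to 7 more (3 to 8 if the missed session's measures are made up). Some graphs will show partial exposure and the overall picture may look less favourable. Some disengaged parents will decline, so only part of the missing evidence is recovered.
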